## **8.2 Sample Size and Power**

The overall study sample size is based on the primary endpoint of ESS measured at days 1-14. The MCID of the ESS is 2.65 and the SD is 5.3 based on previous literature. We assume the MCID and ESS values are the same for both THA and TKA cohorts. 64 patients are needed in the control and intervention groups separately for a two-sided alpha = 0.05, 80% powered study based on an ANOVA for the comparison of the ESS at days 1-14 between the control and intervention group, which provides us a total of 128 patients for THA cohort and TKA cohort separately.

## **8.3 Analysis Datasets**

All patients will be included in the efficacy analyses as randomized (intent-to-treat population). THA cohort and TKA cohort will be analyzed separately throughout.

## **8.4 Description of Statistical Methods**

### **8.4.1 Analysis of the Primary Efficacy Endpoint**

The primary outcome, the ESS score measured at days 1-14 postoperatively for each group, will be summarized using means, standard deviation, median and inter quartile ranges. In the main analysis, the ESS score of the control and intervention group in either THA or TKA cohort will be compared using repeated measures ANOVA. Significant tests will be two-sided at significant level at 0.05.

The normality assumption of the primary efficacy outcome will be checked and strategies to transform the outcome variable will be considered. As a sensitivity analysis, the ANOVA will be replaced with the Wilcoxon rank sum test to ensure the robustness of the results.

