## **2 Objectives and Purpose**

### **2.1 Primary Objective**

The primary objective is the Epworth Sleep Score used to evaluate the impact of melatonin use on the quality of sleep, including total hours of sleep and nighttime awakenings in patients undergoing elective primary total hip and knee arthroplasty.

Secondary Objectives are to monitor and investigate hospital length of stay, and narcotic consumption patterns, scores in patients who take melatonin as a sleep aid for 14 days after surgery.

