## **3 Study Design and Endpoints**

### **3.1 Description of Study Design**

This will be a single-center randomized double blind placebo control clinical trial. In the cohort of patients undergoing primary elective total hip and the cohort of patients undergoing primary elective knee arthroplasty, participants are recruited from those who are willing to consent and participate in the study, and will be randomly 1:1 divided into intervention group and placebo group.

Knee cohort:

- Intervention group will receive a 5mg Melatonin prescription for 14 days
- Control group will receive a placebo pill for 14 days

Hip cohort:

- Intervention group will receive a 5mg Melatonin prescription for 14 days
- Control group will receive a placebo pill for 14 days

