# **Statistical Considerations**

## **8.1 Statistical Hypotheses**

- Primary endpoint: The null hypothesis is that there is no difference between the melatonin and placebo group in the mean ESS score from days 1-14 postoperatively. The alternative hypothesis is that there is a difference between the melatonin and placebo group in the mean ESS score during any of these time points
- Secondary endpoints:
  - Hours of sleeping measured each day from days 1-14 for overnight sleep: The null hypothesis is that there is no difference between the melatonin and placebo group in the mean hours of sleeping at these time points. The alternative hypothesis is that there is a difference between the melatonin and placebo group in the mean hours of sleeping at these time points. Nighttime awakenings are those that require an additional dose of pain medication to go back to sleep.
  - Other secondary endpoints to be listed

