### **8.4.7 Multiple Comparison/Multiplicity**

Not applicable

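### The primary ESS test is not coherently defined: the null concerns the days 1–14 mean, the alternative any day, and no ANOVA term or rule linking the two cohorts to the single objective is stated

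*Combined protocol and SAP*

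**What the plan says.** Section 2.1 gives one primary objective, the effect of melatonin on sleep "in patients undergoing elective primary total hip and knee arthroplasty". Section 8.1 gives one primary hypothesis, not split by joint. Its null is "no difference between the melatonin and placebo group in the mean ESS score from days 1-14 postoperatively"; its alternative is "a difference between the melatonin and placebo group in the mean ESS score during any of these time points".

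The design and analysis sections work by joint. Section 3.1 randomises "In the cohort of patients undergoing primary elective total hip and the cohort of patients undergoing primary elective knee arthroplasty", each with its own intervention and control group. Section 8.2 arrives at 64 per arm, "which provides us a total of 128 patients for THA cohort and TKA cohort separately". Section 8.3 adds that the "THA cohort and TKA cohort will be analyzed separately throughout".

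For the main analysis, 8.4.1 states that "the ESS score of the control and intervention group in either THA or TKA cohort will be compared using repeated measures ANOVA", two-sided at 0.05. As a sensitivity analysis it replaces the ANOVA with a Wilcoxon rank sum test. Section 8.4.7, on multiplicity, reads "Not applicable".

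**The concern.** There are two gaps, and the first is the more serious.

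**Which contrast is primary.** A repeated measures ANOVA with 14 daily values gives a group effect, a time effect and a group-by-time interaction, and invites day-by-day comparisons. Section 8.4.1 does not say which of these answers the primary question. Section 8.1 gives a null that matches the group effect and an alternative that matches a search over days. The rank sum test compares one value per patient, and no such value is named. An analyst could follow the plan and declare the primary result on a single day, or on a term that does not test the stated null.

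**What a result in one joint supports.** The objective joins hip and knee patients; the tests are separate. Nothing says whether the objective is met by a significant result in one joint, only in both, or whether each joint has its own claim. A positive result in one joint could therefore be reported as meeting the joint objective, with no stated error control for that claim.

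**Working it through.** **1. The plan's own sample size (8.2).** Inputs: difference 2.65, SD 5.3, two-sided 0.05, 80% power. The standardised effect is 2.65/5.3 = 0.50. A two-group t-test needs 63.77 per arm, rounded up to 64, with power 80.1%. The stated figure is reproduced. It is the size for one comparison of two groups, on one value per patient, at the full 0.05 in each cohort.

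**2. Hypotheses against model terms.**
- The null in 8.1 (equal mean ESS over days 1–14) is tested by the group main effect.
- The alternative in 8.1 (a difference at any time point) corresponds to 14 day-specific contrasts.
- Group-by-time asks whether the difference changes over days. A constant benefit would not show there, so it does not test the stated null.

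Only the group effect fits both the null and the sample size. The alternative does not fit either.

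**3. Error if any single day counts.** Assume 14 daily tests, each unadjusted at two-sided 0.05, with equal correlation ρ between days. The documents give no correlation, so a range is shown. Under no effect,

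error = 1 − ∫ φ(u) [Φ((1.96 − √ρ·u)/√(1−ρ)) − Φ((−1.96 − √ρ·u)/√(1−ρ))]^14 du.

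| Assumed ρ | Error per cohort |
|---|---|
| 0.5 | about 35% |
| 0.7 | about 25% |
| 0.8 | about 20% |
| 0.9 | about 14% |

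At ρ = 1 the 14 tests are the same test and the error is 5%.

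**4. Error across the two joints, one test per joint.** The cohorts contain different patients and bilateral surgery is excluded (4.2), so the tests are treated as independent.
- A win in either joint suffices: 1 − 0.95² = 9.75% two-sided. In melatonin's favour it is 1 − 0.975² = 4.94%, against 2.5% for one test.
- Both joints must win: 0.05² = 0.25% if neither joint has an effect, and at most 5% if one does.
- Each joint carries only its own claim: 5% per claim.

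**5. Cost of Hochberg, if an either-joint claim is wanted.** Both cohorts are significant if both p-values are at most 0.05; otherwise a cohort is significant only if its p-value is at most 0.025. Two-sided error is 0.05² + 2 × 0.025 × 0.95 = 5.0%. At 64 per arm and SD 5.3, power is 0.8015 at 0.05 and 0.7118 at 0.025; the difference is 0.0896 before rounding.
- Both joints respond: 0.7118 + 0.0896 × 0.8015 = 78.4% per cohort.
- Only one responds: 0.7118 + 0.0896 × 0.05 = 71.6%.

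These figures treat 5.3 as the SD of a patient's 14-day mean, which holds only at ρ = 1. With equal correlation, the SD of the mean is 5.3 × √((1 + 13ρ)/14). At ρ = 0.7 this is 5.3 × √(10.1/14) = 4.50, the standardised effect is 2.65/4.50 = 0.589, and the one-joint figure rises to 85.7%.

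**The case against.** The strongest case is that the plan describes two parallel comparisons. Section 3.1 lists a knee cohort and a hip cohort, each with its own arms. Section 8.2 sizes each in full, 8.3 keeps them apart, and 8.4.5 separates even the baseline tables. In 8.4.1 the word *either* most naturally means *each*. On that reading the multiplicity entry is consistent, and the error is 5% per claim. The hypothesis in 8.1 names neither joint and can be read as a template applied to each cohort. Most of this stands. A reader might infer that the trial's error rate is 9.75%; the documents do not support that, because no passage says that a win in either joint is enough. Nor do they support saying that an alpha adjustment is required.

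It can also be said that the group effect is the obvious intention, since the null and the sample size both point to it. That is fair, and it is why the repair is simple. But the alternative in 8.1 says something else, 8.4.1 does not choose, and the rank sum test has no defined input. Good intent does not settle which result counts once the data are seen.

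A single pooled test with surgery type as a factor would match one joint objective more directly. It would contradict 8.3, so it is not proposed here.

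**Conclusion.** The point holds. The null and alternative in 8.1 do not match, no model term is named, the sensitivity test lacks an input, and the multiplicity entry does not close the gap. The size is conditional: about 14% to 35% per cohort if any single day counted, under assumed equal between-day correlations of 0.9 to 0.5 and unadjusted daily tests. A reader might infer that the plan orders 14 daily tests and so has this error; it does not. The wording of the alternative leaves that route open.

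The question of the two joints is secondary. The text fits separate claims at 5% each. The 9.75% (4.94% in melatonin's favour) applies only if a result in one joint were reported as meeting the single objective in 2.1.

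A reader might also infer that the trial is too small. The power figures do not show that: they assume 64 per arm in each joint, and the lowest of them rests on a between-day correlation of 1.

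**What to change.** Settle the following before unblinding.

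1. **Sections 8.1 and 8.4.1.** In each cohort, make the melatonin–placebo difference in mean ESS over days 1–14 (the group main effect) the only primary contrast. Restate the alternative as a difference in that mean. Label group-by-time and day-specific results descriptive. Apply the Wilcoxon test to each patient's days 1–14 mean.
2. **Section 8.4.7.** Replace the present entry with a rule such as: *each cohort carries only its own claim at two-sided 0.05, and no combined hip-and-knee claim rests on a significant result in one cohort alone.* If the sponsor wants a result in either cohort to meet the single objective, specify Hochberg across the two primary tests instead.

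**Cost.** Wording only, taking 3.2.1 at its word that ESS is evaluated over days 1–14. The separate-claims rule loses no power. Under Hochberg at 64 per arm, per-cohort power falls from 80.1% to 78.4% if both joints respond, or to 71.6% if one does. That is the worst case (between-day correlation of 1), and any statement of these figures in 8.2 should say so.

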### **8.4.2 Analysis of the Secondary Efficacy Endpoints**

The secondary endpoints include number of total hours of sleep, number of nighttime awakenings, and narcotic consumption.

### **8.4.3 Safety Analyses**

AE's will be recorded according to the Medical Dictionary for Regulatory Activities, counted once per individual occurrence, presented in terms of its severity and relationship to AE, and its start date, stop date, severity, relationship, outcome and duration will be reported. All AE's will be ascertained via PI report.

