#### **4.4 Duration of Study Participation**

Participants will be enrolled for approximately 2months after surgery.

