### **6.2 Study Schedule**

Procedure	Screening/Visit 1 (SOC visit within - 3 months of surgery)	Surgery	Visit 2 (SOC visit within +2 months of surgery)
-----------	---	---------	--

Screening	X (Research only)		
Consent	X (Research Only)		
Medical History	X (SOC)		
Surgical History	X (SOC)		
Demographics	X (SOC)		
Distribute medication		X (Research Only)	
Collect pill bottle			X (Research Only)
Collect Adverse Events			X (Research Only)
Collect Questionnaires and peri-operative data (in-patient opioid consumption, Epworth and Stanford sleepiness scale, VAS Pain Scale)		X (Research Only)	X (Research Only)
Collect Sleep Diary			X (Research Only)

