## **7.3 Time Period and Frequency for Event Assessment and Follow-Up**

The occurrence of an AE or SAE may come to the attention of study personnel during study visits and interviews of a study participant presenting for medical care, or upon review by a study monitor. All AEs including local and systemic reactions not meeting the criteria for SAEs will be captured on the appropriate RF. Information to be collected includes event description, time of onset, clinician's assessment of severity, relationship to study product (assessed only by those with the training and authority to make a diagnosis), and time of resolution/stabilization of the event. All AEs occurring while on study must be documented appropriately regardless of relationship. All AEs will be followed to adequate resolution.

Any medical condition that is present at the time that the participant is screened will be considered as baseline and not reported as an AE. However, if the study participant's condition deteriorates at any time during the study, it will be recorded as an AE. UPs will be recorded in the data collection system throughout the study.

Changes in the severity of an AE will be documented to allow an assessment of the duration of the event at each level of severity to be performed. AEs characterized as intermittent require documentation of onset and duration of each episode.

The PI will record all reportable events with start dates occurring any time after informed consent is obtained until 7 (for non-serious AEs) or 30 days (for SAEs) after the last day of study participation. At each study visit, the investigator will inquire about the occurrence of AE/SAEs since the last visit. Events will be followed for outcome information until resolution or stabilization.

All unresolved adverse events should be followed by the investigator until the events are resolved, the subject is lost to follow-up, or the adverse event is otherwise explained. At the last scheduled visit, the investigator should instruct each subject to report any subsequent event(s) that the subject, or the subject's personal physician, believes might reasonably be related to participation in this study.

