## **8.5 Measures to Minimize Bias**

### **8.5.1 Enrollment/Randomization/Masking Procedures**

Research assistants not involved in the study protocol will be responsible for maintaining the patient database and randomization algorithm. Treatment will begin on postoperative day zero. The control groups will receive 14 placebo pills. The treatment group will receive 14 pills of 5mg melatonin. Patients will begin taking a daily pill for 14 days postoperatively. They will continue to receive their selected treatment during their inpatient hospital stay.

Block randomization will be done through RedCap to ensure equal distribution of intervention vs control subjects. The block size will be undisclosed. There will be no stratification based on age, gender, or surgery type.

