#### **11.3.2 Consent Procedures and Documentation**

Informed consent is a process that is initiated prior to the individual's agreeing to participate in the study and continues throughout the individual's study participation. Extensive discussion of risks and possible benefits of participation will be provided to the participants and their families. Consent forms will be IRB-approved and the participant will be asked to read and review the document.

The informed consent process will take place at a pre-surgery clinic visit prior to the day of surgery or in the holding area on the day of surgery. If consenting occurs on the day of surgery, the study team will ensure that efforts are made so patients have enough time to make an informed decision to enroll in the study. A study coordinator, not associated with the surgery, will be the one to introduce the study to the patient in the holding area and patients will be given the opportunity to enroll in the study after the surgery is complete.

The Informed Consent Form (ICF) will be thoroughly explained in a private room with any and all questions addressed prior to signing the ICF. In the event additional time to make an informed decision is required, patient(s)/subject(s) will be able to take a copy of the ICF home for further review and discussion with their friends and family. During the course of the consenting process, subjects will interact with all study personnel. The participant will sign the informed consent document prior to any procedures being done specifically for the study. The participants may withdraw consent at any time throughout the course of the trial. A copy of the signed informed consent document will be given to the participants for their records. The rights and welfare of the participants will be protected by emphasizing to them that the quality of their medical care will not be adversely affected if they decline to participate in this study.

A copy of the signed informed consent document will be stored in the subject's research record. The consent process, including the name of the individual obtaining consent, will be thoroughly documented in the subject's research record. Any alteration to the standard consent process (e.g. use of a translator, consent document presented orally, etc.) and the justification for such alteration will likewise be documented.

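### The safety table counts adverse events per occurrence, with no arm split, no number of patients affected and no on-treatment window, although dosing fills only about 8–21% of the recording window

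*Combined protocol and SAP*

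**What the plan says.** Section 8.4.3 is the whole of the planned safety analysis. Events are "counted once per individual occurrence, presented in terms of its severity and relationship to AE", and for each event "its start date, stop date, severity, relationship, outcome and duration will be reported". It names no treatment arm, denominator, safety population or time window.

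The recording window is in section 7.3: events with onset "any time after informed consent is obtained until 7 (for non-serious AEs) or 30 days (for SAEs) after the last day of study participation". The same section adds that "AEs characterized as intermittent require documentation of onset and duration of each episode".

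Four other places fix the length of that window:
- Section 6.2 puts screening and consent at a visit up to 3 months before surgery.
- Section 11.3.2 allows consent "at a pre-surgery clinic visit prior to the day of surgery or in the holding area on the day of surgery".
- Section 8.5.1: "Treatment will begin on postoperative day zero", with one pill daily for 14 days.
- Section 4.4: "Participants will be enrolled for approximately 2months after surgery".

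Elsewhere the plan does specify arms. Section 8.4.5 tabulates baseline data by melatonin and placebo within each cohort, and section 8.4.1 compares the arms on the Epworth score. The intent-to-treat set in section 8.3 is defined for efficacy only.

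**The concern.** The safety question for a 14-day supplement is whether more melatonin than placebo patients have the effects named in section 1.4.1: dizziness, headache, nausea and sleepiness. These are mild, can recur and are common after surgery in any case. Followed as written, section 8.4.3 gives a tally of events by severity and relationship, and such a tally does not answer that question.

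There are three separate weaknesses:
- **No arm.** Without a split by arm there is no comparison.
- **Wrong unit.** Occurrences are not independent within a patient, so a few patients with repeat events can drive the count. No patient-level incidence is requested.
- **Wrong clock.** The window is tied to consent and the end of participation, not to the drug. Events before the first pill and weeks after the last go into the same tally.

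If these choices are left until the data are in, the window and the counting unit will be chosen with the results in view.

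**Working it through.** **The plan's own figure.** The documents give no figure for the safety analysis. The only related number is the sample size in section 8.2. With difference 2.65, SD 5.3, two-sided 0.05 and 80% power, n per arm = 2 × (1.96 + 0.84)² × (5.3/2.65)² ≈ 63 by the normal formula and 63.8 by the t-test. The stated 64 per arm per cohort is reproduced, which gives 128 per arm over both cohorts.

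**Window and dosing share.** Inputs: dosing 14 days (8.5.1); participation after surgery about 60 days (4.4); tail 7 or 30 days (7.3); lead-in 0 days (11.3.2) to about 90 days (6.2).

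Window = lead-in + 60 + tail. Share = 14 / window.

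| Events | Lead-in | Window | Dosing share |
|---|---|---|---|
| Non-serious | 0 | 67 | 14/67 = 20.9% |
| Non-serious | 90 | 157 | 14/157 = 8.9% |
| Serious | 0 | 90 | 14/90 = 15.6% |
| Serious | 90 | 180 | 14/180 = 7.8% |

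**Dilution.** Assume a constant background rate and a drug effect confined to the 14 dosing days. Observed ratio = 1 + share × (true ratio − 1).
- True ratio 2, non-serious: 1.09 to 1.21. Serious: 1.08 to 1.16.
- True ratio 1.5, non-serious: 1.04 to 1.10.

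**If events cluster after surgery.** Dosing-period events make up half the total once the daily rate in those 14 days is (window − 14)/14 times the rate elsewhere. That is 53/14 = 3.8 times for the 67-day window and 143/14 = 10.2 times for the 157-day window (5.4 and 11.9 times for serious events). At a 50% share, a true ratio of 2 still shows as 1.5.

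**Counting unit.** If each episode of an intermittent event is a separate occurrence, one patient dizzy on 14 nights adds 14 counts, as many as 14 patients dizzy once. In an arm of 64 that is 1/64 = 1.6% of patients against 14/64 = 21.9%, with the same tally. If the episodes are one event, the patient adds one count. The wording does not settle which applies.

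**Illustrative simulation.** The documents give no event rates, so these are assumptions: 0.2 dosing-period events per placebo patient, gamma-distributed differences between patients (shape 0.5 or 1), a true doubling during dosing, and a dosing share of 9% or 21%. There were 3,000 simulated trials per setting.

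| Analysis | Detects doubling, 128 per arm | Detects doubling, 64 per arm |
|---|---|---|
| Patients with ≥1 dosing-period event | 51–64% | 27–37% |
| Full-window event count, patient-level variance | 7–19% | 6–13% |

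The first two analyses have false-positive rates of about 5%. Treating full-window events as independent raises that rate to 16–40%. With a 50% dosing share, the full-window count at 128 per arm detects the doubling in 36–45% of trials, so much of the loss depends on how events are spread over time.

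**The case against.** The strongest defence is that the plan already holds what is needed. Start and stop dates are reported, individual data are listed (8.4.8), and conditions present at screening are baseline, not events (7.3). Section 7.2.2 lists the lack of a temporal relationship as a ground for classing an event as not related, so a headache two months before the first pill should fall in that category. Randomisation means that off-drug events cannot favour an arm. Safety is not a listed objective and no safety test is planned.

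Much of this stands. An on-treatment, per-patient table by arm could be derived, and the contrast is not biased. But that shows only that the better table is feasible. Relationship coding does not replace a comparison by arm, because section 7.2.2 also accepts a temporal relationship alone as grounds for related, and placebo events can meet that. The section 8.4.8 listing is by measure and time, not by arm.

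The window is also less firm than the arithmetic suggests. Three months is the maximum lead-in. Section 6.2 marks event collection only at Visit 2, within 2 months, and section 5.1.8 refers to a 2-week visit. If follow-up ended there after day-of-surgery consent, the dosing share would be 14/21 = 67%.

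A reader might infer that most recorded events would be off drug, that they would swamp any melatonin effect, or that the trial would report no safety difference whatever the truth. The documents support none of these. They show mostly off-drug time, not mostly off-drug events. They give no event rates, and dosing starts on the day of a joint replacement, when events are likely to be frequent.

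**Conclusion.** The point holds in a limited form. Section 8.4.3 states a counting rule that, as written, gives neither the number of patients affected, nor a comparison by arm, nor a window matched to a 14-day drug. Dosing covers about 9–21% of the non-serious window and 8–16% of the serious one, taking 2 months as 60 days and 3 months as 90.

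The ratios of 1.09–1.21 for a true doubling are what a constant background rate would give. Clustering after surgery moves them upward. The effect is dilution and noise, not bias toward either arm. How far repeat events inflate the tally depends on what counts as an occurrence, which the plan leaves open. The primary efficacy analysis is not affected.

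**What to change.** Rewrite section 8.4.3 as follows:
- **Main table:** number and percentage of patients with at least one event, by arm and by hip or knee cohort, among patients who took at least one pill.
- **Window:** onset from the first pill to 7 days after the last (30 days for serious events). Where pill dates are missing, use the surgery date plus 14 days.
- **Named lines:** dizziness, headache, nausea and sleepiness.
- **Supplementary tables:** occurrence counts, and events with onset outside the window. State whether an episode of an intermittent event counts as an occurrence.
- **Wording:** the relationship should be to the study agent, as in section 7.2.2.

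The tail days still dilute somewhat. Under a constant rate, with the effect confined to dosing, a doubling would show as (14 × 2 + 7)/21 = 1.67 for non-serious events and (14 × 2 + 30)/44 = 1.32 for serious ones. Both are well above the full-window values, and the tail allows for late-reported or delayed events.

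The cost is a little more programming and one addition to data collection: the dates of the first and last pill. Section 5.1.8 only encourages return of the bottle, so the dates need their own field. Treatment, visits and sample size do not change.

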## **1.4 Potential Risks & Benefits**

### **1.4.1 Known Potential Risks**

Short term use of melatonin is safe, even in extreme doses with only mild adverse effects which can include dizziness, headache, nausea and sleepiness. Randomized clinical studies have indicated that even long-term exogenous melatonin only mild adverse effects such as dizziness and headaches comparable to placebo.

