## **6 Study Procedures and Schedule**

### **6.1 Study Procedures/Evaluations**

#### **6.1.1 Study Specific Procedures**

- Medical history- a patient's medical history will be elicited during their pre-operative indication for surgery by their operative surgeon. This information will be then accessed via the EMR
- Medication history- current medications will be elicited during the patient's pre-operative indication for surgery by their operative surgery. This information will then be accessed via the EMR
- Physical examination- the patient's height and weight at each visit will be recorded, as well as a targeted physical musculoskeletal examination of the affected joint (ie hip for THA and knee for TKA). This information will then be accessed via the EMR
- Pre- and postoperative sleep survey,
- Survey on quality of sleep,
- Sleep diary
  - To be kept every day for the first 2 weeks
- VAS
- Opioid consumption will be measured based on in-patient pain medications given following surgery. This data will be pulled from Epic following discharge.

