#### **Visit 2 (standard of care post-operatively visit within 2 months of surgery)**

- Observe patient's recovery from TJA surgery as per standard of care
- Record participant's adherence to treatment program.
- Record patient standard sleepiness scale, PROMIS – Sleep Disturbance, VAS pain scores, collect sleep diary and opioid consumption.

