### **7.3.1 Adverse Event Reporting**

Any AE's encountered during the study will be identified by research personnel and brought to the attention of the PI. After investigation by the PI of the surrounding circumstances they will then be reported as quickly as possible, within 1 week, to the IRB, as indicated

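### Adverse events have one scheduled collection point, at an undefined time from about 2 weeks to 2 months after surgery, so mild effects during the 14 dosing days are likely to be under-reported and poorly dated

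*Combined protocol and SAP*

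**What the plan says.** **Schedule.** In the section 6.2 table, the row "Collect Adverse Events" is marked under Visit 2 only. Nothing is marked at screening or surgery, and the table has no column between surgery and Visit 2. Section 6.2.3 describes Visit 2 as a "standard of care post-operatively visit within 2 months of surgery". Besides adherence, its data instruction is "Record patient standard sleepiness scale, PROMIS – Sleep Disturbance, VAS pain scores, collect sleep diary and opioid consumption". Adverse events are not in that list.

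**Source of events.** Section 8.4.3 says "All AE's will be ascertained via PI report". Section 7.3.1 describes a wider route: "Any AE's encountered during the study will be identified by research personnel and brought to the attention of the PI". Section 7.3 has the investigator ask at each study visit about events since the previous one, and adds presentation for care and monitor review. Section 6.2.5 has unscheduled contacts entered in the electronic medical record (EMR), which the team checks regularly.

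**Detail required.** Section 8.4.3 requires start date, stop date, severity, relationship, outcome and duration. Section 7.3 also requires onset and duration for every episode of an intermittent event.

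**Expected effects.** Section 1.4.1 lists mild effects: "dizziness, headache, nausea and sleepiness".

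**Diary.** Section 6.1.1 has patients complete a sleep diary, "To be kept every day for the first 2 weeks". No symptom or adverse event item is described for it.

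**The concern.** The effects the protocol expects are mild and would arise over a two-week course taken partly at home. The plan wants each event dated and its duration reported, yet schedules a single look back, at a visit whose timing is not fixed. A passing headache or spell of dizziness in the first week may be forgotten or only vaguely placed by the time anyone asks. It may also never prompt the patient to contact the hospital.

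At stake is the quality of the tolerability data. Low counts could reflect weak ascertainment as easily as good tolerability, and the dates and durations required by section 8.4.3 would rest on memory. The primary efficacy analysis is not affected.

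**Working it through.** The plan gives no adverse event rate, capture rate or safety sample size, so there is no figure of its own to reproduce on this point. The check is date arithmetic followed by a comparison of sections.

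**1. Recall interval**

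Inputs:
- First dose on postoperative day 0 (section 8.5.1).
- One pill nightly for 14 days (section 5.1.5), so the last dose is on day 0 + 14 − 1 = 13.
- Earliest plausible Visit 2: day 14. Section 5.1.8 has the bottle returned at a 2-week visit, section 8.4.4 has bottles collected at the first postoperative visit, and section 6.2 puts bottle collection in the Visit 2 column.
- Latest Visit 2: 2 months (section 6.2), taken as day 60. The Protocol Summary also puts participation at roughly 60 days.

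Formula: days since last pill = Visit 2 day − 13. Days since first pill = Visit 2 day − 0.

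| Visit 2 on day | Days since last pill | Days since first pill |
|---|---|---|
| 14 | 14 − 13 = 1 | 14 |
| 30 | 30 − 13 = 17 | 30 |
| 60 | 60 − 13 = 47 | 60 |

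The documents allow this whole range. Even at the short end, an event on the first night is recalled two weeks later.

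**2. What covers the dosing days**

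- Inquiry at each study visit (7.3): the schedule has no study visit between surgery and Visit 2, so this adds no query during dosing.
- Identification by research personnel (7.3.1): covers events that staff encounter, and sets no time at which they ask.
- Presentation for care and EMR review (7.3, 6.2.5): reach only patients who make contact.
- Inpatient stay (8.5.1, with examination and vital signs in the EMR under 7.1): gives clinical observation in the early days only.
- Sleepiness scales (3.2.1, 6.2): cover one of the four expected effects, provided the Epworth scale is completed across days 1 to 14 as 3.2.1 states.
- Diary (6.1.1): daily, but with no symptom item described.

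Dizziness, headache and nausea after discharge therefore have no structured daily source.

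**3. Sections that do not agree**

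- Whether Visit 2 collects adverse events: marked in the 6.2 table, absent from the 6.2.3 list.
- When the visit occurs: about 2 weeks (5.1.8; first postoperative visit in 8.4.4) against any time up to 2 months (6.2).
- Who ascertains events: the investigator by inquiry (7.3), research personnel (7.3.1), PI report (8.4.3).

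**4. Effect of incomplete capture**

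Let the true event proportions be p₁ (melatonin) and p₀ (placebo), and let a fraction c of events be captured in both arms. The observed proportions are c·p₁ and c·p₀. Their difference is c(p₁ − p₀), which shrinks in size when c is below 1. Their ratio stays p₁/p₀, but on fewer events. The documents give none of c, p₁ or p₀, so the size of the loss cannot be calculated.

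**The case against.** The strongest reply is that the plan has more capture than section 8.4.3 suggests. PI report may simply be the last step of a route that starts with research staff, visit inquiry and EMR checks. Bottle collection shares a column with adverse event collection, and sections 5.1.8 and 8.4.4 point to a visit near 2 weeks, so recall may be short. The first doses are taken under inpatient observation, and sleepiness is measured by the scales anyway. Section 8.4.3 is also descriptive and plans no test between arms.

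Most of this stands as mitigation. It rules out reading 8.4.3 as though nobody but the PI ever hears of an event. It also rules out treating two months as the expected recall time, because that is only the outer limit. It does not close the gap. Nothing ties adverse event inquiry to a 2-week visit, the schedule permits a much later one, and no listed route asks patients at home about mild symptoms while they are taking the pills.

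A reader might go further and infer that the undercount would make melatonin look safer than it is relative to placebo. The documents do not support that. The trial is double-blind and both arms follow the same procedures, so the loss should be similar in each.

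**Conclusion.** The point holds as a modest weakness in safety ascertainment. There is one scheduled collection at an undefined time, no structured query during dosing, and a demand for dates and durations that this arrangement is poorly placed to meet. Mild transient effects are likely to be under-reported and imprecisely dated.

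The measurable part is a recall interval of about 1 to 47 days after the last pill. This assumes dosing on days 0 to 13, a 2-month limit of 60 days and an earliest visit on day 14. A reader might infer that these events will certainly be missed, or try to put a number on those lost. The documents support a likelihood only, and give no rates from which a number could be derived.

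The expectation of similar loss in both arms rests on the blind holding; section 8.5.2 plans no evaluation of that. On that footing the consequence is lower counts and less precision in both arms. This is an inexpensive improvement and does not threaten the trial's main conclusion.

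**What to change.** 1. Add to the existing 14-day diary a brief daily item for dizziness, headache and nausea, plus one free-text line. Sleepiness can be left to the sleepiness scales.
2. List adverse event inquiry in the Visit 2 text of section 6.2.3, to match the section 6.2 table.
3. Reword section 8.4.3 so that events are ascertained from the diary, direct inquiry at each contact and the EMR.
4. Report the number of patients with at least one event, by arm within each cohort. Section 8.4.3 counts occurrences only, and section 8.3 keeps the hip and knee cohorts separate throughout.
5. Reconcile sections 5.1.8, 6.2 and 8.4.4 on visit timing, and sections 7.3, 7.3.1 and 8.4.3 on who ascertains events.

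**Cost:** one diary block, one table and some text edits. Patients do slightly more each day, and staff will have more mild events to process. No extra visit, procedure or participant is needed.
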